### 9.7.3 Questionnaire analysis

The general statistical considerations described above (§9.7.1) will be applied for quantitative and qualitative variables. The number of missing data will be indicated. Missing values are expected to be few and distributed at random. Since there is no applicable method unanimously accepted, there will be no replacement or imputation of missing data (13).

Confidence intervals of 95% will be evaluated for endpoint variables.

Physicians' answers will be analysed by subgroups of physician's specialty per country, and on the overall dataset.

For each question associated to the outcomes included in the main objective, a criterion will be calculated to separate physicians with an appropriate answer (or at least one appropriate response if the corresponding question allows multiple answers or is an open-ended question). These proportions of appropriate answers will be expressed among physicians with complete web-questionnaires.

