### 8.2 OBJECTIVE

The survey objective is to measure the effectiveness of the DHPC and EM, implemented as part of RMMs, by ascertaining the proportion of targeted physicians who understood and implemented the latest prescribing conditions and safety information about systemic thicolchicoside provided in the DHPC and EM.

Specific objectives were to evaluate the proportion of physicians who:

- prescribe systemic thicolchicoside only as adjuvant treatment of painful muscle contractures associated with acute spinal pathology in adults and in adolescents from 16 years onwards.
- do not prescribe systemic thicolchicoside for long-term treatment of chronic conditions.
- follow the recommendations regarding the doses and duration restriction:
  - for oral forms: the recommended and maximal dose is 8 mg every 12 hours, i.e. 16 mg per day. The treatment duration is limited to 7 consecutive days.
  - for IM forms: the recommended and maximal dose is 4 mg every 12 hours, i.e. 8 mg per day. The treatment duration is limited to 5 consecutive days.
- do not prescribe systemic thicolchicoside during pregnancy and lactation.
- do not prescribe systemic thicolchicoside in women of childbearing potential not using adequate contraception.

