### 4) Prescribing conditions and safety information/warnings of systemic thiocolchicoside containing medicinal products:

- Knowledge of the prescribing conditions and safety information about systemic thiocolchicoside presented in the DHPC and EM:
  - Indication
  - Contraindicated conditions
  - Recommended maximal dose, posology and duration of use for oral and IM forms
  - Information to be communicated to a patient before prescribing the drug
  - Specific information to be advise to females of childbearing potential

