#### 4.3 Contraindications

[the wording below should be inserted]

Thiocolchicoside must not be used

- in patients hypersensitive to the active substance or to any of the excipients listed in section 6.1
- during the entire pregnancy period
- during lactation
- in women of childbearing potential not using contraception.

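### Section 9.7.3 counts one appropriate response as enough on multiple-answer and open-ended questions, so those per-question proportions overstate understanding of the restrictions

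*Protocol*

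**What the plan says.** Section 8.2 sets the objective as estimating "the proportion of targeted physicians who understood and implemented the latest prescribing conditions and safety information". It then lists the restrictions one by one: use only in the stated indication and age group, no long-term use in chronic conditions, dose and duration limits by form, no use in pregnancy and lactation, and no use in women of childbearing potential without adequate contraception.

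Section 9.7.3 says how answers become a proportion: "For each question associated to the outcomes included in the main objective, a criterion will be calculated to separate physicians with an appropriate answer". In brackets it extends this to the case "or at least one appropriate response if the corresponding question allows multiple answers or is an open-ended question". The denominator is also fixed: "These proportions of appropriate answers will be expressed among physicians with complete web-questionnaires".

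Some knowledge topics in section 9.3, item 4, have several parts by content, for example "Recommended maximal dose, posology and duration of use for oral and IM forms" and "Information to be communicated to a patient before prescribing the drug". Contraindicated conditions and advice to females of childbearing potential are listed there too.

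Section 9.7.1 refers to correct and appropriate answers without defining them. The ENCePP checklist in Annex 2 (sections 3 and 6) states that no specific endpoints are defined. Section 9.7.3 is therefore the only operational scoring rule in the protocol.

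**The concern.** The restrictions in section 8.2 are cumulative and exclusionary: use only in this indication, and not in these patients. A rule satisfied by any one appropriate response tests neither feature. If contraindications are asked as one multiple-answer question, a physician who names pregnancy and omits lactation and contraception passes. If the indication is asked that way, a physician who selects the acute indication together with a chronic one passes. A physician who ticks every option passes with certainty.

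The level of these proportions carries the conclusion. Section 9.7.1 plans no statistical comparison and explains that a before-after design is not possible. With no reference value, the definition of an appropriate answer largely determines how well the letter and educational materials seem to have worked. Section 8.1 singles out pregnancy, lactation and contraception, and these are restrictions that a single question could collapse into one pass.

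**Working it through.** **1. The plan's own figure.** Section 9.5.2 uses n = P(1 − P)z²/e². With P = 0.5, z = 1.96 and e = 0.04, n = 0.25 × 3.8416 / 0.0016 = 600.25, which matches the stated 600. The scoring rule does not affect this: P = 50% is already the largest-variance case, so n stands under any scoring. The 4-point half-width describes sampling error. The problem here is one of definition, which a larger n would not reduce.

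**2. Number of required parts, k.** The documents do not give the question formats, so k is an assumption guided by content. The English SmPC text in Annex 5 (SmPC section 4.3) lists four contraindications: hypersensitivity, pregnancy, lactation, and use "in women of childbearing potential not using contraception". The summary of the English letter in Annex 4 names the last three. I use k = 4 and k = 3.

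**3. What holds without assumptions.** Let p₁, …, p_k be the shares of physicians giving each required part.
- P(at least one) ≥ the largest p_j.
- P(all) ≤ the smallest p_j.

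So the at-least-one proportion is never below the best-known part and never below complete knowledge. Ignoring wrong choices can only widen the gap to a criterion that disqualifies them.

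**4. Illustration with independent parts.** Take every p_j = 50%. This borrows the protocol's planning value and is not a forecast.
- P(at least one) = 1 − (1 − p)^k. For k = 4: 1 − 0.5⁴ = 93.75%.
- P(all) = p^k. For k = 4: 0.5⁴ = 6.25%.

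**5. Illustration with correlated parts.** Parts communicated in the same letter are likely to be known together. I use a beta-binomial model with correlation ρ between parts and s = (1 − ρ)/ρ:
- P(all) = ∏ (ps + i)/(s + i), for i = 0 to k − 1.
- P(at least one) = 1 − ∏ ((1 − p)s + i)/(s + i).

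For k = 4 and ρ = 0.5, s = 1 and P(all) = (0.5 × 1.5 × 2.5 × 3.5)/(1 × 2 × 3 × 4) = 6.5625/24 = 27.3%. At p = 50%, P(at least one) = 1 − 0.273 = 72.7%.

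| Parts k | Correlation ρ | At least one | All |
|---|---|---|---|
| 4 | 0 | 93.75% | 6.25% |
| 4 | 0.2 | 85.7% | 14.3% |
| 4 | 0.5 | 72.7% | 27.3% |
| 4 | 0.8 | 59.1% | 40.9% |
| 3 | 0 | 87.5% | 12.5% |
| 3 | 0.5 | 68.75% | 31.25% |
| 3 | 0.8 | 57.5% | 42.5% |

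With equal p, the two rules agree only under perfect correlation.

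**6. Can the planned tables recover complete knowledge?** The mock table in section 9.7.1 gives a count for each answer, that is, each p_j separately. With four parts at 50%, complete knowledge can lie anywhere between max(0, 4 × 0.5 − 3) = 0% and 50%. The per-answer counts therefore do not determine it. Nor do they show how many physicians combined right and wrong answers.

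**The case against.** Four points on the other side carry weight.

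- **The questionnaire is not shown.** Annex 1 lists it as a stand-alone document, and section 9.3 lists topics, not formats. If pregnancy, lactation and contraception are separate single-answer questions, the rule does not touch them. This stands: the number of affected questions is unknown.
- **Single restrictions remain visible.** The mock table in section 9.7.1 reports each answer by specialty and country, and free text is to be grouped by theme and listed by frequency. A reader might infer from 9.7.3 that the survey cannot detect a restriction that failed to get through. The documents do not support that, since a poorly known option would show in its own row. What is missing is the share with complete knowledge and the share mixing right with wrong answers.
- **Other data address behaviour.** Section 9.3, item 6, collects indication, dose, duration and reproductive status for up to five recent prescriptions. This helps, although section 9.9.4 warns of recall and selection bias in those data, and it does not correct the knowledge proportions.
- **A blanket all-correct rule would also mislead.** In an open recall question, a physician may know an element and not write it down. Some items, such as sources of knowledge, have no correct set. This stands and shapes the fix.

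It could also be said that scoring keys belong in the statistical analysis plan, and section 9.8.2 does foresee composite indicators. But the protocol does not leave the rule open. It fixes one, and nothing else in the protocol replaces it.

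**Conclusion.** The point holds for every multiple-answer or open-ended question that is linked to the main objective and has more than one required part. For those questions the reported proportion overstates understanding of the section 8.2 restrictions. The direction needs no assumption about correlation. The size cannot be stated from the documents: for four parts each known by 50%, the gap between the two rules runs from about 88 points with independent parts to about 18 points at correlation 0.8. All values of k, p and ρ are assumed.

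A reader might infer that a single headline result is inflated and that the study is thereby tipped to a verdict of effective. The protocol does not support this. It defines no single endpoint and no success threshold, and its analysis is descriptive. Nor should 94% against 6% be read as the expected size, since it is the independent-parts case. Single-answer questions and the sample size of 600 are unaffected. The rule should be changed, but it does not invalidate the survey: SHOULD-FIX.

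**What to change.** Amend section 9.7.3 as follows, before the data are analysed.

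- For each multiple-answer question with a defined correct set, pre-specify the required and the disqualifying responses, taken from the DHPC and EM.
- For closed multiple-answer questions, define an appropriate answer as all required responses given and no disqualifying one.
- For open-ended questions, report the proportion naming each required element and the distribution of the number named.
- Keep the at-least-one proportion only as a measure labelled partial knowledge.
- Exclude from correct/incorrect scoring the items with no correct set, such as sources of knowledge.

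The cost is one revised rule, a scoring key and a few more table rows. No new data and no change in sample size are needed. The reported proportions can be expected to be lower on the affected questions.

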## 9.8 QUALITY CONTROL

### 9.8.1 Approaches for validating the questionnaire

The questionnaire will be tested among 6 physicians for its comprehensibility, consistency and the appropriateness of medical terms. The questionnaire will be translated from English into local language using the back and forth method to ensure an accurate translation of the local versions of the questionnaire will be validated by the MAHs.

### 9.8.2 Approaches for validating the results

The quality control for validating the results will be conducted at five levels:

- 1) At IMS Medical Radar management level, every efforts will be undertaken to collect complete and valid data:
  - Verification of the reliability and security of the web questionnaire interface by a qualified web-master for each country,
  - Monitoring of the quality and datasets definition by a qualified data manager. In the background of the web questionnaire, real-time checks of the answers provided by the respondents will be developed. Non admissible answers (i.e. incorrect or unusual values, outlying values) will be detected and queries sent to the physician.
- 2) At the study database level (after merging datasets of each country), final data quality checks will be applied (beyond data management process):
  - Distribution of each variable in order to count the number of missing values and estimate the associated relative percentage,
  - Identification and count of non-analysable questionnaires:
    - estimation of the percentage of physicians without complete analysable questionnaire.

Any changes in the database will be tracked and documented. The country-datasets will be stored in a dedicated database. Once data validated and quality checked, the database will be locked.

- 3) At the statistical analysis level: all data management and statistical analysis programs developed and used in the analysis will be documented. All versions generated will be dated, kept with accompanying documentation and archived. The original database will be stored. A derived database will be created for the new versions of the data in order to include recoding and computing of new variables, especially stratification of continuous variables, combination of modalities for categorical variables, calculation of composite indicators, etc.
- 4) At the results level, a data review will be done to ensure data integrity. A statistical analysis report including all the results will be provided for review and discussion. The final statistical report will take into account the reviewers' comments.
- 5) At the study level, all aspects of the study will be conducted according to the SOPs of IMS Real World Evidence Solutions and IMS Medical Radar divisions.  
The study documents have been approved by people competent in medical and safety areas of IMS. According to the SOPs, an independent review of the survey results and report will be conducted by a person who was not in charge of their preparation.

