### 5) Awareness of and attitude towards the latest prescribing conditions and safety information:

- Awareness of the prescribing conditions and safety information about systemic thiocolchicoside presented in the DHPC and EM:

- Awareness of the prescribing conditions and safety information: main concerns perceived
- Sources of knowledge
- Reception of the DHPC by the physician and awareness about the EM
- Physician's intention to consider the prescribing conditions and safety warnings

6) Recent prescriptions details:

The following information related to up to the last five prescriptions to patients will be collected upon physician's recall memory:

- Approximate date of prescription of systemic thiocolchicoside
- Approximate patient' age at the time of prescription (age ranges: <16 or ≥16 years old)
- Gender
- Status at the visit for females of childbearing potential (using or not an effective method of contraception, pregnant or not, planning to be pregnant, breastfeeding)
- Indication for which the drug was prescribed
- Form, number of administrations and dose per administration per day
- Duration of use prescribed
- Concomitant treatment(s) ongoing or written at the time of prescription
- Main reasons for choosing systemic thiocolchicoside
- Information and recommendations provided to the patient when prescribing systemic thiocolchicoside containing medicinal products.

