## **9.6 DATA MANAGEMENT**

The survey will be conducted according to the Standard Operating Procedures (SOPs) of IMS Medical Radar and IMS Real World Evidence Solutions.

Collected data will be entered and stored in a database specific to the survey and the country. A study database will be created by merging of databases of each country.

Data will be checked in terms of consistency before data analysis:

- removal of duplicates (if required),
- data labelling and data formatting,
- range and consistency checks for each variable to identify potential non admissible values,
- cross-check the consistency of data for related variables (if feasible).

The number of variables with missing values will be indicated. Missing values are excluded from the calculation of percentages.  
The study database will be locked once validated.

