Free text answers to open-ended questions will be categorised by theme, listed according to the frequency.

Confidence intervals of 95% will be evaluated, when relevant.

The proportions of correct and appropriate answers to selected questions asked in the questionnaire will be expressed among physicians with complete analysable web questionnaires. The endpoint will be assessed overall, by country and among subgroups of physicians' specialty.

In a first step, calculations will be performed on raw data. No projection factor will be applied to generalize the results to the entire prescribers' universe. As a consequence, the line "Overall - unweighted results" will show only the results observed on the overall sample, and will not reflect the countries' universe since this sample is not proportional to the size of IMS OneKey reference files in each country.

In a second step, the results will be weighted according to the real proportion of physicians in each specialty and country in order to accurately reflect the population that the survey seeks to measure.

For each country, the results will be reported according to the prescribers' specialty distributed proportionally to their weight within IMS OneKey reference lists.

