## 9.9 STRENGTHS AND LIMITATIONS OF THE RESEARCH METHODS

### 9.9.1 Strengths:

#### 1) use of IMS OneKey reference lists of physicians

The IMS OneKey file used to target interviewed physicians is an international database that cover more than 80 countries and 8.5 millions of HCPs/health facilities. In each country, the database is fully representative of the HCPs population.

The information contained in the file of each country is updated constantly with proactive updates. Quality controls are implemented on a regular basis.

2) The sampling of physicians follows a stratified randomised method which guarantees the representativeness of the contacted population in order to limit selection bias due to voluntary participation. Batches of physicians will be contacted up to five times before moving forward to other physicians in the lists.

3) The questionnaire includes general questions followed by specific ones in order to limit a learning process during the survey. It included both open- and closed questions. As the physicians may understand the right answer in subsequent questions, it would not be possible to go back in the questionnaire and edit answers in former questions.

The questionnaire is tested for its clarity and absence of questions raisons social desirability bias. The translation of the questionnaire is tested before implementation.

4) The study is conducted by an experienced team specialised in the design and conduct in such survey in safety area. It follows IMS SOPs (14) as well as the methodological guidelines on ENCePP and EMA GVP.

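### The live query rule in section 9.8.2 exempts no scored item, so wrong dose and duration answers could be prompted for correction and the proportion correct biased upward

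*Protocol*

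**What the plan says.** Section 9.8.2, in the data manager's part of the first quality-control level, says that behind the web questionnaire "real-time checks of the answers provided by the respondents will be developed", and then: "Non admissible answers (i.e. incorrect or unusual values, outlying values) will be detected and queries sent to the physician". Section 9.6 lists, among the checks before analysis, "range and consistency checks for each variable to identify potential non admissible values".

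Section 9.7.1 defines what is reported: "The proportions of correct and appropriate answers to selected questions asked in the questionnaire". Section 9.7.3 adds that each outcome question is scored by whether the physician's answer was appropriate. The knowledge items in section 9.3 include "Recommended maximal dose, posology and duration of use for oral and IM forms". The prescription details in the same section include dose per administration, number of administrations and prescribed duration.

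Section 9.9.1 recognises that physicians may work out the right answer as they proceed, and gives this as the reason why "it would not be possible to go back in the questionnaire and edit answers in former questions".

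On traceability, section 9.8.2 says "Any changes in the database will be tracked and documented" and that the original database is kept. Section 10.3.2 adds an audit trail. No section says whether the answer before or after a query is the one analysed.

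**The concern.** In most data collection, an incorrect or outlying value is a data error and a query repairs it. Here it may be the finding. A stated maximal dose above the label, or a reported duration beyond the limit, is a wrong answer or a departure from the prescribing conditions. Section 8.2 sets out to count exactly these. A query on such a value tells the physician that something is amiss and invites a second attempt.

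The resulting error would mostly run one way, towards concluding that the DHPC and EM worked. Recruiting more physicians would not reduce it, and it could not be undone after fieldwork unless first answers had been kept and used. Section 9.9.3 already names social desirability and the copying of online information as threats in a web survey. A query on a scored item gives both an opening.

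**Working it through.** **1. Reading the passages together**

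- *Trigger.* Section 9.8.2 spells out what counts as non-admissible: incorrect, unusual or outlying values.
- *Timing.* The checks run in real time, while the physician is answering.
- *Scope.* Section 9.8.2 exempts no item, and section 9.6 applies its range and consistency checks to every variable.
- *Overlap with the endpoint.* Dose and duration are numeric, can be outlying, and are scored. They are where the rule and the endpoint meet.
- *Data-cleaning reading.* Suppose the word incorrect means only invalid. Unusual and outlying values are still queried, and an outlying dose or duration is still an outcome.
- *Relation to 9.9.1.* If the query comes after the physician has moved on, acting on it requires the editing that 9.9.1 rules out. If it comes on the current screen, the letter of 9.9.1 is kept, but the form itself supplies the hint that 9.9.1 is meant to prevent.

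**2. The plan's own precision (section 9.5.2)**

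n = P(1 − P) z² / e². With P = 0.50, z² = 3.8415 and e = 0.04: 0.25 × 3.8415 / 0.0016 = 600.2. This reproduces the stated 600. The figure is not in dispute and serves as the yardstick.

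**3. Size of a possible bias**

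Let p be the true proportion correct and c the share of wrong answers that are both queried and changed to correct. Assume that no correct answer is changed to a wrong one. Then

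expected observed proportion = p + (1 − p)c, and bias = (1 − p)c.

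The protocol gives no value for c, so a range is shown. At p = 50%:

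| c (assumed) | Observed | Bias (points) |
|---|---|---|
| 0 | 50.0% | 0 |
| 5% | 52.5% | 2.5 |
| 8% | 54.0% | 4.0 |
| 10% | 55.0% | 5.0 |
| 20% | 60.0% | 10.0 |
| 30% | 65.0% | 15.0 |

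**4. The c at which the bias equals the half-width**

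c = 1.96 √(p(1 − p)/600) / (1 − p).

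| p | Half-width (points) | c needed |
|---|---|---|
| 30% | 3.67 | 5.2% |
| 50% | 4.00 | 8.0% |
| 70% | 3.67 | 12.2% |
| 90% | 2.40 | 24.0% |

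**5. Effect on coverage (unweighted Wald interval, n = 600, p = 50%)**

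At c = 8% the observed proportion centres on 0.54, with standard error √(0.54 × 0.46 / 600) = 0.0204. The bias is 0.04 / 0.0204 = 1.97 standard errors, so the nominal 95% interval covers the true value about 50% of the time. The same calculation gives about 77% at c = 5% and 31% at c = 10%.

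**The case against.** The strongest reply is that the trigger is non-admissibility, not disagreement with the label. The sentence sits among a data manager's tasks, and section 9.6 uses the same term beside duplicate removal, labelling and formatting. Correctness is scored later, in the analysis, and nothing suggests that the web form holds an answer key. Section 9.3 also provides for recording patients who are pregnant, breastfeeding or not using contraception, so the form is built to accept prescriptions outside the label. The questionnaire is a separate document, and item-level edit checks may be set there or in operating procedures. Database changes are tracked.

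Much of this stands, and it rules out stronger readings that a reader might take from the wording:

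- *That wrong answers will be prompted and the result is inflated.* The protocol does not say which items are queried, that an admissible off-label answer is among them, or that a queried answer may be changed.
- *That 9.8.2 flatly contradicts 9.9.1.* A query on the entry being made can coexist with a bar on going back. The two are in tension.
- *That patient age is affected in the same way.* It is recorded only as "age ranges: <16 or ≥16 years old". The lower band is a planned response category and cannot be a numeric outlier. The case rests on dose and duration.
- *That a bias of 4 points is expected.* The c of 8% is simply the value that makes the bias equal the half-width. The planned 50% is also a worst-case sizing assumption, not a forecast for a dose question.

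The reply does not remove the point itself. The protocol is not silent here: it states a rule, in terms that cover unusual and outlying values on every item. Traceability would allow changes to be examined, but it does not settle which answer counts.

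**Conclusion.** The concern holds as a risk created by an unrestricted rule, not as a demonstrated bias. As written, section 9.8.2 allows scored dose and duration answers to be queried during completion, and it weakens the protection that section 9.9.1 claims as a strength.

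The size depends wholly on c. It is zero if no scored answer is queried or if the first answer is analysed. At a true 50%, a c of 8% would use up the planned 4-point half-width, and at higher true proportions a larger c is needed. These figures assume that changes run only from wrong to correct, and the coverage figures ignore the weighting. The planned sample of 600 is unaffected.

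**What to change.** Before launch, amend sections 9.8.2 and 9.6 as follows:

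- On knowledge items and prescription details, limit live queries to impossible, malformed or blank entries and to neutral unit or consistency checks that do not reveal the label.
- State that no query or range limit is triggered by disagreement with the labelled dose, duration, age, indication or contraindications.
- Store the first submitted answer to every scored item and make it the one analysed.
- Reconcile the wording of 9.6, 9.8.2 and 9.9.1, so that non-admissible has one meaning and it is clear when, if ever, an answer can be changed.

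The cost is protocol wording and the programming of the web-form checks. The downside is that a few genuine keying errors stay in the data.
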